## 6 OBJECTIVES AND ENDPOINTS

### 6.1 Objectives

#### 6.1.1 Primary Objectives

The primary objectives of the study are to:

- Identify an optimal dose of moxidectin for the treatment of scabies.
- Evaluate the safety of moxidectin in adults infected with scabies.

#### 6.1.2 Secondary Objective

The secondary objective of the study is to characterize the plasma pharmacokinetic of moxidectin in adults infected with scabies.

#### 6.1.3 Exploratory Objectives

The exploratory objectives of the study are to:

- Describe the impact of moxidectin on *S. scabiei*, including impact on morphology, motility and life cycle stages.
- Evaluate clinician and patient reported outcomes of treatment with moxidectin.

### 6.2 Endpoints

#### 6.2.1 Primary Endpoints

The primary endpoints of the study are:

- Efficacy will be determined by death of the mites, defined as the degradation (loss of internal and/or external anatomic structures) of the adult mite observed by RCM. Mites will be assessed at Hours 4, 8, 24, 48 and 72 and Days 7, 14 and 28 in not less than two lesions nominated pre-treatment.
- Safety will be assessed by the incidence and severity of AEs, physical examinations, and measurement of vital signs up to and including Week 12, and laboratory safety parameters up to and including Day 28.

#### 6.2.2 Secondary Endpoints

Key exposure metrics for moxidectin including area under the concentration time curve (AUC) and maximum plasma concentration ( $C_{max}$ ), will be determined by non-compartmental analysis of moxidectin pharmacokinetic parameters or other methods as appropriate, assessed up to and including Day 28.

#### 6.2.3 Exploratory Endpoints

The exploratory endpoints of the study are:

- At Hours 4, 8, 24, 48 and 72 and Days 7, 14 and 28, using assessment by RCM of burrows selected pre-treatment:
  - Changes in adult mite motility (peristalsis and/or movement) over at least 30 seconds of observation.
  - Presence, number, morphology and motility of juvenile scabies mites.
  - Presence of eggs and scybala in burrows
- Presence and total number of mites and burrows assessed visually at Days 7, 14 and 28.

- Changes in assessment of clinician-reported scabies symptomology, including extent of symptoms on body regions assessed by the number of anatomically-defined regions affected, number of lesions and severity grading of excoriations and erythema.
- Changes in patient reported outcomes, measured by Numerical Rating Scale, 5-D Itch Scale and Dermatology Life Quality Index.

## 7 STUDY DESIGN

### 7.1 Study Design

This is a randomized, double-blind, multicenter, parallel group, dose finding study of a single oral dose of moxidectin in adults with scabies.

### 7.2 Dosing Regimens

Initially, subjects will be randomized with a target allocation ratio of 1:1:1 to one of the following single dose treatment regimens:

- Moxidectin 2 mg
- Moxidectin 8 mg
- Moxidectin 20 mg

Once approximately three subjects have been recruited to these three dose cohorts and completed their Day 14 visit, a Protocol Steering Committee (see [Section 13](#)) will evaluate the unblinded safety and efficacy data and recommend:

- Continuation of the study with no dose modification to the target sample size of 6 subjects per cohort; or,
- Stopping recruitment of one or more of the current dose cohorts; and/or,
- The addition of a 36 mg single dose cohort.

Once the Committee has made their recommendation, randomization will continue into the same or revised dosing regimens with a final target sample size of 6 subjects per cohort. It is anticipated that a maximum of 36 subjects will be included in the study.

### 7.3 Study Sites

This is a multicenter study.

### 7.4 Estimated Duration of the Study

The study is expected to take approximately 18 months to complete. The on-study period per subject is 13 weeks, consisting of one week for Screening and 12 weeks post-treatment.

## 8 SUBJECT POPULATION

### 8.1 Selection of Subjects

The nature of the study and the potential risks will be explained to all candidates. Written informed consent will be obtained from each subject prior to performing Screening procedures.

Subjects who meet all of the inclusion and none of the exclusion criteria described in [Sections 8.2](#) and [8.3](#) will be eligible for randomization. Once randomized, subjects will be considered enrolled and will receive treatment with moxidectin. Once randomized, subjects will not be permitted to be re-randomized or given a second course of treatment.

Inclusion and exclusion criteria are to be assessed at the Screening assessment, unless otherwise indicated.

### 8.2 Inclusion Criteria

A subject must meet all of the following inclusion criteria:

1. Aged  $\geq 18$  years.
2. Provision of written informed consent.
3. Parasitologically confirmed active *Sarcoptes scabiei* infestation, defined as the presence of at least two lesions (which may include burrows), each containing at least one live (internal and/or external structures discernable) adult *Sarcoptes scabiei* mite observed by RCM.
4. Agree to the use of reliable contraceptive measures if female or male partner of a female of child-bearing potential from Screening until 6 months after treatment with study drug ([Section 8.4.2](#)).

### 8.3 Exclusion Criteria

A subject will be excluded from the study if they meet any of the following criteria:

1. History of chronic or recurring dermatologic disease (other than scabies) that could interfere with the diagnosis and/or subsequent clinical assessment of scabies.
2. Diagnosis of crusted/Norwegian scabies or scabies that, in the opinion of the Investigator, would require treatment with more than one standard of care (e.g. scabies requiring concurrent topical and oral treatment).
3. Received any treatment for scabies within 7 days of Screening, including but not limited to permethrin, ivermectin, benzyl benzoate, lindane, crotamiton, malathion, and/or tea tree oil.
4. Presence of any other clinically relevant condition, including infection, immunological disorder, malignant disease, and/or other underlying condition or circumstance at Screening or Baseline that would put the subject at increased risk from participating in the study or confound study evaluations.
5. Poor venous access.
6. Received an investigational agent within 28 days of Screening (or 5 half-lives of the investigational agent, whichever is longer).
7. Body Mass Index over 35 kg/m^2.
8. Clinically relevant abnormal findings in vital signs, 12-lead ECG, or physical examination at Screening and/or Baseline in the opinion of the Investigator.
9. Clinically relevant laboratory abnormalities at Screening, including:
  - a. alanine aminotransferase or aspartate aminotransferase  $> 2.5$  x upper limit of reference range;
  - b. creatinine  $> 2.0$  milligrams per deciliter (mg/dL);
  - c. hemoglobin  $< 9.5$  g/dL (female) or  $< 10.5$  g/dL (male);

**CONFIDENTIAL**

[figure not shown]
- d. amylase > 2.0 x upper limit of reference range.
10. Known or suspected hypersensitivity to macrocyclic lactones or excipients used in the formulation of moxidectin.
11. Use of systemic steroids within 14 days of Screening, history of prolonged use of systemic and/or high-dose inhaled corticosteroids, or use of topical steroids for 7 out of the 14 days prior to Screening.
12. Subjects with known or suspected *Loa loa* coinfection.
13. Difficulty swallowing tablets.
14. Pregnant or breastfeeding, or planning to become pregnant.
15. Known or suspected alcohol or illicit substance abuse.
16. Unwilling, unlikely or unable to comply with all protocol specified assessments.
17. Previous enrolment and treatment with moxidectin in this study.

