#### 8.4 Other Study Eligibility Criteria Considerations

In order to assess any potential impact on subject eligibility with regard to safety, the Investigator must refer to the relevant document(s) for detailed information regarding warnings, precautions, contraindications, AEs, and other significant data pertaining to the study product(s) being used in this study. Such documents may include the Investigator's Brochure (IB) and the Prescribing Information.

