##### 8.4.1 *Loa loa* Co-Endemicity

Patients with *Loa loa* may develop a serious or even fatal encephalopathy following treatment with macrocyclic lactones, including moxidectin. Moxidectin has not been studied in patients infected with *Loa loa*. It is recommended that individuals who have had exposure to *Loa loa*-endemic areas undergo diagnostic screening for loiasis prior to treatment with moxidectin. *Loa loa* parasites are found in West and Central Africa, including Cameroon, Democratic Republic of the Congo, Gabon, and Nigeria (Figure 1).

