#### 9.3.1 Screening Visit (Day -7 to Day -1)

Subjects will be screened up to 7 days prior to randomization to determine eligibility for participation in the study. Screening assessments may be conducted on different days if required. The following procedures will be performed and documented during Screening:

- Obtain written informed consent prior to any study related procedures (see [Section 16.1.2](#)).
- Parasitological assessment including confirmation of the presence of at least 2 lesions with live adult *S. scabiei* mites for assessment throughout the study by RCM (see [Section 9.4.7](#)).
- Medical history (see [Section 9.4.2](#)).
- A complete physical examination (see [Section 9.4.3](#)) including:
  - assessment of all appropriate body systems to determine study eligibility;
  - measurement of height and weight.
- Vital signs while in the supine position (see [Section 9.4.4](#))
- A 12-lead ECG (see [Section 9.4.5](#))
- Concurrent medication assessment (see [Section 11](#))
- Blood samples drawn for hematology and clinical chemistry (see [Section 9.4.6.1](#))
- Pregnancy test for women of childbearing potential (see [Section 9.4.6.2](#))

CONFIDENTIAL

Results of all Screening tests must be available and reviewed prior to the subject's Baseline visit. Subjects meeting all the inclusion criteria and none of the exclusion criteria will return to the clinic within 7 days of commencement of Screening for randomization into the study.

Subjects will be required to fast overnight (from midnight) prior to the Baseline visit (Day 0). Water may be consumed *ad libitum*.

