### 9.3.2 Baseline (Day 0)

#### 9.3.2.1 Pre-Treatment

Subjects will return to the clinic for final eligibility confirmation through the following assessments:

- Targeted physical examination (see [Section 9.4.3](#)).
- Parasitological assessment (see [Section 9.4.7](#)), which includes:
  - selection of at least 2 (but not more than 4) lesions with live adult *S. scabiei* mites for assessment throughout the study by RCM; and
  - photographs of the selected live adult *S. scabiei* mites using a dermatoscope and RCM.
- Concurrent medication assessment (see [Section 11](#)).
- For women of childbearing potential, confirmation of a negative pregnancy test (see [Section 9.4.6.2](#)).

Subjects meeting all of the inclusion and none of the exclusion criteria will be randomized to a treatment group and then have the following performed:

- Vital signs (see [Section 9.4.4](#))
- Cannulation for collection of blood samples (see [Section 9.4.6.3](#)) for:
  - pharmacokinetic assessments;
  - plasma storage;
  - if Screening was conducted more than 72 hours before Baseline, blood samples should also be collected for hematology and clinical chemistry (see [Section 9.4.6.1](#))
- Assessment of clinical signs of scabies infestation, which includes:
  - mapping, counting and grading of scabies inflammatory and non-inflammatory lesions (see [Section 9.4.8.1](#)); and
  - administration of patient reported outcome questionnaires including the Numerical Rating Scale itch score, 5-D itch score and Dermatology Life Quality Index (see [Section 9.4.8.2](#))
- Adverse event assessment (see [Section 12](#))

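### Loiasis testing is only recommended for subjects exposed to Loa loa areas: exclusion 12 does not cover exposure, and no listed step asks about it or records a test

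*Protocol*

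**What the plan says.** Protocol 8.4.1 states the hazard plainly: patients with Loa loa "may develop a serious or even fatal encephalopathy following treatment with macrocyclic lactones, including moxidectin". It adds that moxidectin has not been studied in people with this infection. It then recommends that individuals who have been exposed to endemic "areas undergo diagnostic screening for loiasis prior to treatment with moxidectin", names four example countries in West and Central Africa, and refers to a prevalence map.

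The operative criterion is exclusion 12 in 8.3: "Subjects with known or suspected *Loa loa* coinfection". It has no cross-reference to 8.4.1. Under 8.1, eligibility for randomization depends on the criteria in 8.2 and 8.3.

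Two other provisions touch the point. Exclusion 4 covers an "underlying condition or circumstance at Screening or Baseline that would put the subject at increased risk from participating in the study" or confound its evaluations. Section 8.4 says that, when assessing safety-related eligibility, the investigator "must refer to the relevant document(s) for detailed information regarding warnings, precautions, contraindications" and similar safety data; the Investigator's Brochure and Prescribing Information are given as examples.

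For conduct, 9.3.1 introduces the Screening list with "The following procedures will be performed and documented during Screening" and says "Results of all Screening tests must be available and reviewed prior to the" Baseline visit. Section 9.3.2.1 opens with "Subjects will return to the clinic for final eligibility confirmation through the following assessments". Neither list names Loa loa.

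**The concern.** The warning and the rule have different triggers. Section 8.4.1 is triggered by exposure, which a symptom-free person can have without anyone suspecting infection. Exclusion 12 is triggered by known or suspected infection, and suspicion is not defined. Nothing in the listed procedures connects the two, because nobody is told to ask where the subject has lived or travelled.

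Several features of this trial make the gap matter:

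- SAP 2.3 plans sites in Australia and France, outside the areas 8.4.1 names. Exposure will come to light only through a question about the past.
- The recruitment rationale in 5.4.3 mentions refugees and the homeless in Europe as groups with higher scabies prevalence, so past residence elsewhere is a realistic possibility.
- Section 5.4.3 expects safety to resemble that in healthy volunteers, on the ground that reactions in onchocerciasis patients came from the host response to dying microfilariae. A subject with undetected Loa loa does not fit that premise.
- There is one oral dose, it cannot be withdrawn, and 5.3.2.1 gives a mean half-life of about 20 to 47 days.

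**Working it through.** The plan gives no figure to reproduce. The check sets the texts side by side, counts the listed procedures and follows one subject through them.

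**1. Warning against rule**

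| | 8.4.1 | Exclusion 12 (8.3) |
|---|---|---|
| Trigger | Exposure to an endemic area | Known or suspected coinfection |
| Action | Diagnostic test before moxidectin | Exclusion |
| Force | Recommendation | Binding through 8.1 |
| Test result needed? | Not made a condition of dosing | Not mentioned |

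**2. Items naming Loa loa exposure or a loiasis test**

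| Place | Items listed | Items naming it |
|---|---|---|
| 9.3.1 Screening | 9 | 0 |
| 9.3.2.1 before randomization | 4 | 0 |
| Table 1 | 18 rows | 0 |
| Table 2 | 13 rows | 0 |
| Table 8 | 7 hematology + 20 chemistry = 27 lines | 0 |

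The inclusion/exclusion row of Table 1 reaches exclusion 12 by reference only. Section 9.4.1 names sex, ethnicity and date of birth, but not country of birth or residence. Section 9.4.2 names diagnosed or recurrent conditions, significant medical or surgical history and a review of body systems. It would pick up diagnosed loiasis, but it does not prompt for exposure.

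**3. One subject followed through**

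Take an adult who once lived in Cameroon, which 8.4.1 names, and who has no symptoms and has never been tested.

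- Demographics and medical history as specified need not reveal the residence.
- The blood tests at Screening are hematology, chemistry and, where applicable, pregnancy. None is a loiasis test.
- Exclusion 12: infection is not known, and nothing elicited has raised suspicion.
- Exclusion 4: it can be applied only if the circumstance is known.
- Baseline adds a targeted examination, mite assessment, medications and, where applicable, pregnancy confirmation.

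Under 8.1 this subject is eligible and can be dosed.

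**4. How the protocol handles another 8.4 consideration**

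For pregnancy, inclusion 4 cross-references 8.4.2. Section 9.4.6.2 lists tests at Screening, Baseline and Week 12 (3 visits) and requires a negative result before dosing. Loiasis has no listed test and no required result.

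**5. Dose context**

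Section 5.3.2 gives 2 to 8 mg as the range in onchocerciasis patients. This trial gives up to 20 mg and possibly 36 mg: 20/8 = 2.5 and 36/8 = 4.5 times the highest dose in those patients.

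**The case against.** The strongest reply is that 8.4.1 and exclusion 12 are meant to be read together. Section 8.4.1 sits under the heading on other eligibility considerations and supplies the risk, the trigger, the action and the geography. An investigator could reasonably treat exposure as suspicion until a test resolves it. The duty in 8.4 to consult the safety documents is mandatory, exclusion 4 is broad, 9.3 allows extra assessments when clinically indicated, and the medical history in 9.4.2 is not a closed list. This shows that the hazard is recognized and that a careful site has ways to act. But every route except the 8.4 duty and the 8.4.1 advice itself works only once exposure is known. Those two could prompt the question, but one depends on documents not supplied and the other is only a recommendation.

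Some of the counts prove less than they seem to. Table 8 is a routine hematology and chemistry panel, and Table 2 starts at Baseline, so zeros there are unsurprising. Other exclusions, such as hypersensitivity, difficulty swallowing and substance abuse, also have no dedicated procedure. That is fair: the Screening list and Table 1 carry the point, and the other zeros only confirm that nothing sits elsewhere. Loa loa differs from those exclusions in that the protocol itself recommends a specific pre-treatment test and cites a possibly fatal outcome.

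The pregnancy comparison can be challenged because loiasis testing is conditional on exposure. Pregnancy testing is conditional too, on childbearing potential, and is still listed. The schedule can evidently carry a conditional test.

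Two limits stand. The CRF, SRM, Investigator's Brochure and model consent form were not available, and any of them might contain a prompt. The trial is also small, at most about 36 subjects, with no stated share exposed. A prompt elsewhere would reduce the practical risk, but it would not change the eligibility criterion.

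**Conclusion.** The concern holds. In the protocol text supplied, a site can complete every listed procedure, apply every criterion as worded, and dose an exposed subject who has not been tested for loiasis. The safeguards that exist are real but discretionary.

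The size can be given only as coverage, meaning that no listed item elicits exposure or records a test. The documents give neither the proportion of exposed subjects nor the risk of encephalopathy in an infected one, so no expected number of events is claimed. The conclusion assumes that 8.1 means what it says about which criteria decide eligibility, and that a recommendation does not bind a site. Sample size, endpoints and analysis are unaffected. The change should be made, because a possibly fatal and avoidable harm is weighed against a small burden.

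**What to change.** - Add a residence and travel history item for the areas described in 8.4.1 to the Screening list in 9.3.1 and to Table 1.
- Reword exclusion 12 to: known or suspected Loa loa coinfection, or exposure to a Loa loa-endemic area (see 8.4.1) without a negative diagnostic test for loiasis documented before randomization.
- So that the criterion can be applied, state in 8.4.1 what counts as exposure and which test is accepted.

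The cost is one question for everyone and, for exposed subjects only, a test the protocol already recommends. Because selection criteria change, 16.1.4 requires an amendment with ethics committee approval. The result must be back before Baseline, within the 7-day Screening window. Under 8.4.3, rescreening for reasons other than laboratory abnormalities needs Sponsor agreement, so an occasional exposed subject may be delayed or not enrolled.

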#### 8.4 Other Study Eligibility Criteria Considerations

In order to assess any potential impact on subject eligibility with regard to safety, the Investigator must refer to the relevant document(s) for detailed information regarding warnings, precautions, contraindications, AEs, and other significant data pertaining to the study product(s) being used in this study. Such documents may include the Investigator's Brochure (IB) and the Prescribing Information.

##### 8.4.1 *Loa loa* Co-Endemicity

Patients with *Loa loa* may develop a serious or even fatal encephalopathy following treatment with macrocyclic lactones, including moxidectin. Moxidectin has not been studied in patients infected with *Loa loa*. It is recommended that individuals who have had exposure to *Loa loa*-endemic areas undergo diagnostic screening for loiasis prior to treatment with moxidectin. *Loa loa* parasites are found in West and Central Africa, including Cameroon, Democratic Republic of the Congo, Gabon, and Nigeria (Figure 1).

**Figure 1 Map of Estimated Prevalence of Eye Worm History in Africa**

Source: World Health Organization/African Programme for Onchocerciasis Control. Online at: <http://www.who.int/apoc/raploa/en/> accessed 07 Sep 2018.

### 8.4.2 Contraception

All women of child-bearing potential (defined as sexually mature women who have had menses within the preceding 24 months and have not undergone hysterectomy, bilateral oophorectomy or tubal ligation) must have a negative pregnancy test at Screening. Pregnancy testing may be performed by analysis of serum or urine and should be confirmed at Baseline prior to study drug administration. Pregnancy testing will be repeated at Week 12.

Women of child-bearing potential must agree not to attempt to become pregnant. If participating in sexual activity that could lead to pregnancy, women of child-bearing potential and male partners of women of child-bearing potential must agree to use a reliable method of contraception during the study and for the 6 months following study drug administration.

Women who are not of reproductive potential (who have been postmenopausal for at least 24 consecutive months or have undergone hysterectomy, bilateral oophorectomy or tubal ligation) are not required to use contraception.

### 8.4.3 Rescreening

Subjects who are determined to be ineligible for the study on the basis of laboratory abnormalities may be re-screened for eligibility once. All other subjects may only be rescreened once discussed and agreed with the Sponsor.

## 8.5 Special Protocol Issues

### 8.5.1 Treatment of Contacts

As untreated contacts may be a source of scabies re-infestation, all close personal contacts of enrolled subjects, including household, family and sexual contacts, will be offered the approved current standard of care scabies treatment.

The participant must be counselled to avoid contact with any treatments taken by their close personal contacts.

